## **MMRM Based on Primary Measures Collected during the Double-blind and Follow-up Periods**

The details for this analysis are provided in Section 7.4.

### **7.3.1.2 Sensitivity Analysis for Possible Violation of Normality Assumption**

The normality test is performed on the residuals which are generated by the same MMRM as used for the primary efficacy analysis. The residuals are scaled by the inverse Cholesky root of its estimated variance-covariance matrix. The Kolmogorov-Smirnov test for normality is applied to the de-correlated and scaled residuals and normality test is rejected if p-value from the Kolmogorov-Smirnov test is less than 0.01.

If the normality test is rejected, the sensitivity analysis uses MI in conjunction with robust regression to assess the robustness of the primary MMRM analysis to the possible violation of normality assumption. This method has been described and referred as ADAP [R] in Mehrotra 2012. The detail of the sensitivity analyses will be provided in the statistical analysis plan.

### **7.3.2 Secondary Efficacy Analyses**

[figure not shown]
The secondary efficacy variables are identified in Section 7.2.2.

The secondary endpoints for headache days, acute medication use days, MSQ v2.1 Role Function-Restrictive domain score, Performance of Daily Activities domain score of the AIM-D, and Physical Impairment domain score of the AIM-D will be analyzed in the same manner as that used to analyze the primary endpoint.

The 50% responder, defined as a participant with at least a 50% reduction from baseline in the 3-month average of monthly migraine days, will be assessed for each individual. A logistic regression model will be used to analyze the 50% responders across the 12-week treatment period. This model assumes a binary distribution for the response and uses a logit link. The analysis model will include treatment group, prior exposure (yes/no) to a migraine prevention medication with proven efficacy, and baseline monthly migraine days. The treatment difference in terms of odds ratio between each atogepant dose group and placebo will be estimated and tested from this model.

The overall type I error rate for multiple comparisons across two atogepant doses and the primary and secondary efficacy endpoints will be controlled at the 0.05 level using a graphical approach by [Bretz 2009](#). The primary endpoint will serve as the gatekeeper for the secondary endpoints. A complete graph and details of the graphical multiple comparison procedure will be presented in the statistical analysis plan of this study.

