## 2. Study Objectives and Clinical Hypotheses

### 2.1 Study Objectives

- To evaluate the safety and tolerability of atogepant 10 mg, atogepant 30 mg, and atogepant 60 mg for the prevention of migraine in participants with EM.
- To prospectively test for superiority of atogepant 10 mg, atogepant 30 mg, and atogepant 60 mg versus placebo for the prevention of migraine in participants with EM.

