#### 7.3.1 Primary Efficacy Analyses

The primary efficacy endpoint is the change from baseline in mean monthly migraine days across the 12-week treatment period. The primary null hypothesis is that atogepant treatment doses (atogepant 10 mg, atogepant 30 mg, and atogepant 60 mg once a day) are each equally effective to placebo in mean change from baseline in mean monthly migraine days across the 12-week treatment period. The alternative hypothesis is that at least 1 of the 3 doses of atogepant has a different effect than placebo.

The primary comparison between treatment groups will be done by a mixed-effects model for repeated measures (MMRM) of the change from baseline. The statistical model will include treatment group, visit, prior exposure (yes/no) to a migraine prevention medication with proven efficacy, and treatment group by visit interaction as categorical fixed effects. It will also include the baseline score and baseline-by-visit interaction as covariates. An unstructured covariance matrix will be used to model the covariance of within-participant repeated measurements. The Kenward-Roger approximation ([Kenward 1997](#)) will be used to estimate the denominator degrees of freedom. The analysis will be performed based on all postbaseline values using only the observed cases without imputation of missing values. Pairwise contrasts in the MMRM model will be used to make the pairwise comparisons of each atogepant dose to placebo.

Only data collected during the double-blind period will be included in the analysis. Participants are always analyzed based on the treatment group assigned by randomization.

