## 7.6 Sample Size Calculation

A total sample size of 218 participants will be randomized per treatment group and that will provide at least 98% power to detect the treatment difference between each of the 3 atogepant doses (assumed equally effective) and placebo for the primary efficacy endpoint. The sample size of this study was selected to provide sufficient power for the primary efficacy endpoint and the first 3 secondary endpoints as shown in [Table 7-1](#). The power calculations are based on the following assumptions:

- 1) The treatment difference from placebo will be similar to the average value across the migraine prevention studies for atogepant (Phase 2/3 Study CGP-MD-01), telcagepant ([Ho 2014](#)) and monoclonal antibodies ([Dodick 2014a](#); [Dodick 2014b](#); [Bigal 2015](#)). The standard deviation of each endpoint was estimated from an internal study that randomized approximately 800 participants. In particular, the assumed treatment difference from placebo in change from baseline in mean monthly migraine days across the 12-week treatment period is -1.5 days, and the standard deviation is 3.5 days. Detailed treatment difference and standard deviation assumptions are listed in [Table 7-1](#).
- 2) The study statistical testing plan controls the overall type I error at 5%. The power calculations of the primary and secondary endpoints have taken the multiple comparisons into consideration by testing each dose versus placebo at a 0.0167 significance level, 2-sided.

A detailed graphical multiple comparison procedure will be presented in the statistical analysis plan.

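### Does the protocol's reference to two atogepant doses leave one of the three doses outside the 5% type I error rate?

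*Protocol*

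**What the plan says.** Protocol 7.3.2 (Secondary Efficacy Analyses) states that the "overall type I error rate for multiple comparisons across two atogepant doses and the primary and secondary efficacy endpoints" is to be controlled at 0.05 by a graphical procedure. It adds: "The primary endpoint will serve as the gatekeeper for the secondary endpoints". The full graph is left to the SAP.

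Elsewhere the plan has three doses:

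- Protocol 2.1 gives the efficacy objective: "To prospectively test for superiority of atogepant 10 mg, atogepant 30 mg, and atogepant 60 mg versus placebo".
- Protocol 5.4 randomises equally to placebo and three active arms, 218 in each.
- Protocol 7.3.1 names all three doses in the primary null hypothesis and continues: "The alternative hypothesis is that at least 1 of the 3 doses of atogepant has a different effect than placebo". SAP 10.2 says the same.
- Protocol 7.6 claims its power for all three doses and allows for multiplicity by "testing each dose versus placebo at a 0.0167 significance level, 2-sided", under an overall error rate of 5%. The Protocol Summary and SAP 15 give the same level.
- SAP 15 adds that, once a dose's primary comparison succeeds at 0.0167, its secondary endpoints are tested in sequence.

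**The concern.** The sentence in 7.3.2 is the one place in the protocol that defines the controlled family by both doses and endpoints. It is current body text, legible and not redacted. With three doses and seven endpoints (one primary, six secondary) there are 3 × 7 = 21 comparisons with placebo. Taken literally, a two-dose family covers 2 × 7 = 14 of them. The other seven would fall outside, and nothing says which dose they belong to.

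The other literal reading is that alpha is divided by two, 0.025 per dose, while three doses are tested. The error rate could then exceed 5%. Protocol 1.3 presents the study as pivotal and intended for registration, so an ambiguous error family would be a serious matter if it were real.

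**Working it through.** **Inputs.** Overall alpha 0.05 (Protocol 7.3.2, 7.6); per-dose alpha 0.0167 two-sided (Protocol 7.6, SAP 15); 218 per arm, equal allocation (Protocol 5.4, 7.6); effects, standard deviations and responder rates from Protocol Table 7-1.

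**1. Which split does 0.0167 represent?** 0.05/3 = 0.01667, or 0.0167 to four decimals. 0.05/2 = 0.025. The stated level is the three-way split. A two-dose family at 0.0167 each would spend only 2 × 0.0167 = 0.0334, leaving 0.0166 with no use.

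**2. Do the stated powers fit that level?** For means, power = Φ(δ / (σ√(2/n)) − z), where z is the two-sided critical value: 2.393 at 0.0167 and 2.241 at 0.025. For the primary endpoint, 3.5 × √(2/218) = 0.3352 and 1.5/0.3352 = 4.474. Then Φ(4.474 − 2.393) = Φ(2.081) = 0.981. The responder rates use the two-proportion formula with pooled variance under the null.

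| Endpoint | Inputs | Stated | At 0.0167 | At 0.025 |
|---|---|---|---|---|
| Migraine days | −1.5, SD 3.5 | 98% | 98.1% | 98.7% |
| Headache days | −1.5, SD 3.8 | 95% | 95.8% | 97.0% |
| Acute medication days | −1.2, SD 3.2 | 93% | 93.6% | 95.3% |
| 50% responders | 33% vs 50% | 89% | 89.0% | 91.6% |

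The stated figures are the 0.0167 values with the decimals dropped. At 0.025 the last two rows miss by 2.3 and 2.6 points. The secondary powers are conditional on earlier success with endpoints assumed independent, so the single-endpoint values are the right comparison.

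**3. Error over the three primary comparisons.** The sum is 3 × 0.05/3 = 0.05 (0.0501 with the rounded level). If the comparisons were independent it would be 1 − (1 − 0.0167)³ = 0.0493. Equal arms sharing one placebo group give a pairwise correlation of 0.5, and simulation with 4 million draws then gives 0.0446.

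**4. The inflated case.** At 0.025 for all three doses the sum is 3 × 0.025 = 0.075, and the simulated value with the shared placebo is about 0.065. No section of either document sets 0.025.

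**5. Secondary endpoints.** If each dose's secondaries are tested in fixed sequence after its primary at the same level, as SAP 15 describes, the error for a dose across its seven endpoints stays at or below 0.05/3. The sum over doses is again 0.05.

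**The case for a change.** The strongest case for acting is that a confirmatory trial's family statement should need no interpretation. The SAP does not openly correct it, because SAP 19 lists no changes from the protocol. The section that would settle the secondary endpoints, Table 10-1 and Figure 10-1 of the SAP, cannot be read in the public text.

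Part of this stands. The wording is wrong, and how alpha passes between doses and endpoints in the graph cannot be checked here. The rest does not carry. An entry of no changes in SAP 19 fits a slip as well as it fits a two-dose family, since the SAP carries forward the protocol's three hypotheses and its 0.0167 level. The table and figure are listed in the SAP's contents, so the procedure was specified; text missing from the public copy is not evidence against it. The paragraph just before the disputed sentence in 7.3.2 also compares every dose group with placebo on the responder endpoint, which does not fit a deliberate restriction to two doses.

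**Conclusion.** This is a clerical slip: 7.3.2 says two where the plan has three. An analyst following the hypotheses, the per-dose level and SAP 15 would test three doses at 0.0167 each. The primary familywise error is then at most 0.05 by the sum of the levels, and about 0.045 with the shared placebo arm. The figures of 0.065 and 0.075 belong to a 0.025 rule that nobody has written down.

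Reading the word as three leaves the alpha levels, the 218 per arm, the powers and every possible conclusion as they are, so no change to the plan follows. The conclusion assumes equal arms, approximately normal test statistics, and a graph in the SAP that starts from the 0.0167 per dose given in SAP 15. Its detailed propagation to the secondary endpoints is unverified rather than in doubt.

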### 7.3.3 Additional Efficacy Analyses

### 7.3.4 Safety Analyses

MedDRA nomenclature will be used to code TEAEs. Incidence will be tabulated by primary SOC and by specific event within each primary SOC. TEAEs will be analyzed after treatment start on Day 1 through the end of the study. TEAEs will also be summarized separately for the double-blind treatment and follow-up phases of the study.

## 7.4 Off-treatment Hypothetical Estimand

This section defines an estimand, termed as off-treatment hypothetical estimand, [REDACTED]  
[REDACTED]  
[REDACTED]

### 7.4.1 Treatment Condition of Interest

Participants take assigned treatment by randomization during the double-blind treatment period. In addition, permissible and prohibited mediations are described below:

- Participants are allowed to take acute migraine medications (Protocol Section 4.4.1) to keep the participants in the study.
- The protocol prohibits patients from starting any new migraine preventive treatments (Protocol Section 4.4.2) during the study (including the double-blind treatment period and the follow-up period).

### 7.4.2 Population

The target population is patients suffering from migraine with aura or migraine without aura satisfying the inclusion and exclusion criteria as specified in Section 4.

The analysis population is defined to be all randomized participants who received at least 1 dose of study treatment, had an evaluable baseline period of eDiary data and had at least 1 evaluable post-baseline 4-week period (Weeks 1 to 4, 5 to 8, 9 to 12) of eDiary data, regardless of whether on study treatment or off study treatment.

### 7.4.3 Variable

The variable is the same as the primary efficacy endpoint defined in Section 7.2.1, which is the change from baseline in the participant's mean monthly (4-weeks) migraine days across the 12-week treatment period as derived from the eDiary data.

#### **7.4.4 Accounting of Intercurrent Events**

Intercurrent events and their handling rules are as follows:

- Participants who started a new migraine prophylaxis treatment during the double-blind or safety follow-up period will have their data during the safety follow-up period after starting the new migraine prophylaxis treatment excluded from the analysis.
- Participants who discontinue study treatment due to all reasons other than starting a new migraine prophylaxis treatment will have their data collected after discontinuation of study treatment, and those off-treatment data will be included in the analysis.

Detailed methods and procedures will be documented in the statistical analysis plan prior to study completion.

#### **7.4.5 Population-level Summary**

The population-level summary for the primary endpoint is the difference in primary variable means between each atogepant group and placebo.

Participants are always analyzed based on their treatment assignment by randomization. To obtain the estimate of treatment effect defined in the off-treatment hypothetical estimand, a MMRM similar to the primary analysis specified in Section 7.3.1 will be performed on observed data including both on-treatment and off-treatment monthly migraine days.

#### **7.4.6 Off-treatment Hypothetical Estimand Approach for the Secondary Endpoints**

Continuous secondary endpoints will be handled using the same estimand approach defined above for the primary endpoint.

The secondary endpoint of 50% responders will be derived using both on-treatment and off-treatment observed data as defined in the primary endpoint above. The population-level summary for this endpoint is the odds ratio for each atogepant group relative to placebo.

#### **7.5 Subgroup Analyses**

Subgroup analysis based on prior exposure (yes/no) to a migraine prevention medication with proven efficacy will be performed for the following efficacy endpoints:

- Change from baseline in mean monthly migraine days across the 12-week treatment period.
- Change from baseline in mean monthly headache days across the 12-week treatment period.
- Change from baseline in mean monthly acute medications use days across the 12-week treatment period.
- $\geq 50\%$  reduction in 3-month average of monthly migraine days
- $\geq 75\%$  reduction in 3-month average of monthly migraine days
- 100% reduction in 3-month average of monthly migraine days

Subgroup analyses for primary efficacy endpoint based on demographic factors (age, sex, race) will be provided in the integrated summary of efficacy to facilitate the comparison across pivotal studies.

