## **7. Statistical Procedures**

### **7.1 Analysis Populations**

The ITT population will consist of all randomized participants. All efficacy analyses will be performed using the mITT population, consisting of all randomized participants who received at least 1 dose of study intervention, had an evaluable baseline period of eDiary data and had at least 1 evaluable post-baseline 4-week period (Weeks 1 to 4, 5 to 8, and 9 to 12) of eDiary data during the double-blind treatment period. All safety analyses will be performed using the safety population, consisting of all participants who received at least 1 dose of study intervention.

The primary efficacy analysis population [REDACTED] includes all randomized participants who received at least 1 dose of study treatment, had an evaluable baseline period of eDiary data and had at least 1 evaluable post-baseline 4-week period (Weeks 1 to 4, 5 to 8, 9 to 12) of eDiary data during the double-blind treatment period and follow-up period, regardless of whether on study treatment or off study treatment.

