### **7.2 Collection and Derivation of Efficacy Assessments**

On a daily basis during the 28-day baseline period and throughout the study, participants are to record into an eDiary information on the daily total duration of headache, headache specific characteristics and symptoms, the worst pain severity, and use of any acute headache pain medication. Participants will be able to report headache data, including absence of headache, for the day of the eDiary report and for the day immediately prior to the day of the eDiary report, as long as information reported is for a time subsequent to the participant's most recent report. This is defined as a one-day "missing-recall" window.

Following randomization on Day 1, there are 4 visits at 2-week intervals, followed by 2 visits at 4-week intervals; altogether encompassing a 12-week double-blind treatment phase of the study and a 4-week follow-up phase. In practice, there may or may not be exact 2-week or 4-week durations between two consecutive visits and the visits might not align with each

28-day period recorded in the eDiary (ie, Weeks 1 to 4, 5 to 8 and 9 to 12, corresponding to Days 1 to 28, 29 to 56, and 57 to 84). Therefore, for data analysis purposes, the number of migraine days during the last 28 days prior to the randomization date, will serve as the “baseline”, and change from baseline will be calculated for consecutive 28-day periods beginning with the date of first dose of study intervention.

In order to be randomized, a participant should be in the baseline phase for at least 28 days and must report eDiary data for at least 20 days (including missing recall) during the 28-day baseline period. If less than 28 days of baseline data are reported, the number of headache days and other such counting variables for “baseline” will be prorated to standardize the count to a 28-day equivalent. Subsequent to treatment start, the number of headache days will be counted in successive and non-overlapping 4-week (ie, 28-day) windows. Headaches that continue into a subsequent 4-week period will be counted (with recorded severity and duration) as occurring in each period.

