If any postbaseline eDiary window for a participant has at least 14 but less than 28 days of reported data, the prorated approach will be used. If a participant reports less than 14 days of headache data, the participant’s observed counts in that particular 28-day eDiary window will be set to missing for that window. These prorating rules will be applied to all efficacy analyses of eDiary data unless otherwise stated.

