10.2.2 Sensitivity Analysis for Possible Violation of Normality Assumption

10.2.3 Sensitivity Analyses in Missing Data Handling

ANCOVA Model Based on 3-month Average of the Monthly Migraine Days

The response variable for the ANCOVA model is the change from baseline in the 3-month average of the monthly migraine days for each participant. The ANCOVA model includes terms for treatment, prior exposure (yes/no) to a migraine prevention medication with proven efficacy, and baseline score. The treatment difference for atogepant doses versus placebo will be estimated and reported along with the corresponding 95% CI and nominal p-value for superiority testing. This analysis was recommended by FDA at the End of Phase 2 meeting and termed as supportive analysis. There are no missing data based on this derivation because patients who discontinued the treatment are assumed to maintain the same mean (observed while on treatment) for 3 months (12 weeks).

Within-group Imputation Based on Observed Data

Sensitivity analysis will be performed based on imputation using participants from the same treatment group with observed data under the MAR assumption. The details of imputation are as follows

Allergan	SAP 3101-301-002 AGN-241689

MMRM Based on Primary Measures Collected during the Double-blind and Follow-up **Periods**

The details for this analysis are provided in Section 10.5.

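### For the 100% reduction endpoint, a prorated zero stays zero, so gaps in the diary can only push the migraine-free rate up; the effect on the treatment comparison can go either way

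*Protocol*

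**What the plan says.** Protocol 7.5 and SAP 13 list "100% reduction in 3-month average of monthly migraine days" as one of six endpoints to be analysed by prior exposure to preventive medication. It is not among the primary or the six secondary endpoints.

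Protocol 7.2 sets the rule for incomplete diaries. If a post-baseline window "has at least 14 but less than 28 days of reported data, the prorated approach will be used". Below 14 days, the "observed counts in that particular 28-day eDiary window will be set to missing for that window". The scope is wide: "These prorating rules will be applied to all efficacy analyses of eDiary data unless otherwise stated". The text on baseline explains what proration does: counts "will be prorated to standardize the count to a 28-day equivalent". Missing days are limited by a short recall window, since participants can enter data "for the day of the eDiary report and for the day immediately prior to the day of the eDiary report".

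Before randomization the plan asks for more. Protocol 7.2 and 8.3 require at least 20 of the 28 baseline days to be reported.

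No visible text gives the 100% endpoint its own completeness rule. The sections most likely to do so are redacted or largely not shown: Protocol 7.2.3 and 7.3.3, SAP 10.4, and most of SAP 17.2.1.

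**The concern.** Proration is a reasonable correction for a mean count when days are missing at random: one migraine day in 14 reported days becomes two in 28. It cannot correct a zero, and a zero in every window is exactly what this endpoint requires. A participant with no migraine day on 42 reported days (14 per window) is classed the same as one with no migraine day on all 84.

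Within evaluable windows the error goes one way. An unreported migraine day can turn a participant into a 100% responder, but an unreported day can never turn one into a non-responder. At stake is how a migraine-free rate is read: part of it would reflect diary gaps, and arms or subgroups with different completion would not be comparable.

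**Working it through.** **The plan's own figures.** The documents state no rate or power for the 100% endpoint. The stated power figures reproduce: 218 per arm, difference 1.5, SD 3.5 and two-sided alpha 0.0167 give 98.1% (stated 98%); 33% versus 50% gives 89.0% (stated 89%). Neither involves the endpoint discussed here.

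**Single-participant check (no model for migraine frequency).** Suppose a participant has exactly one migraine day in 84, and the reported days are a random subset. The chance that it falls on an unreported day, so that the participant is scored as a 100% reduction, is (84 − n)/84. That is 50% at n = 42 and 21% at n = 66 (22 per window). With two migraine days and n = 42 it is (42 × 41)/(84 × 83) = 25%.

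**Population illustration: inputs.**
- Difference of 1.5 days: Protocol 7.6.
- Monthly means of 5.0 (placebo) and 3.5 (atogepant): assumed, chosen to differ by 1.5.
- SD of the 28-day count, 3.5: borrowed from Protocol Table 7-1, where it is the SD of a change from baseline. This is an assumption, varied below from 3.0 to 4.0.
- Unreported days missing at random, with the same number reported in each window: assumed.

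**Model.** Daily migraine is beta-binomial with parameters a and b. With p = mean/28, rho = [SD²/(28p(1 − p)) − 1]/27 and a + b = 1/rho − 1. Then P(no migraine day in n reported days) = B(a, b + n)/B(a, b).

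- Atogepant: p = 0.125, 28p(1 − p) = 3.0625, rho = (12.25/3.0625 − 1)/27 = 1/9, so a = 1 and b = 7. The formula reduces to 7/(7 + n).
- Placebo: p = 5/28, 28p(1 − p) = 4.107, rho = (12.25/4.107 − 1)/27 = 0.0734, so a = 2.253 and b = 10.365.

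| Reported days per window (n in total) | Atogepant | Placebo | Risk difference | Odds ratio |
|---|---|---|---|---|
| 28 (84) | 7/91 = 7.7% | 0.8% | 6.9 points | 10.7 |
| 24 (72) | 7/79 = 8.9% | 1.0% | 7.8 points | 9.2 |
| 21 (63) | 7/70 = 10.0% | 1.4% | 8.6 points | 8.1 |
| 14 (42) | 7/49 = 14.3% | 2.9% | 11.4 points | 5.6 |

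At 21 days per window, 1 − 7.7/10.0 = 23% of those scored as 100% responders on atogepant would not be migraine-free over all 84 days.

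**Sensitivity to the SD.** For SD 3.0 to 4.0, the atogepant rate is 3.3% to 13.5% with complete diaries and 4.9% to 16.3% at 21 days per window.

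**Less extreme gaps.** If 10% of each arm report 14 of 28 days and the rest report fully, the atogepant rate is 0.9 × 7.7 + 0.1 × 14.3 = 8.4% and the risk difference is 7.4 points.

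**Unequal gaps.** With atogepant complete and placebo at 21 days per window, the risk difference falls from 6.9 to 7.69 − 1.36 = 6.3 points; with placebo at 14 days it falls to 7.69 − 2.88 = 4.8 points. With no drug effect, equal gaps create no difference between arms.

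**The case against.** The strongest objection concerns the treatment comparison. A reader might infer from the rising risk difference that the rule inflates the drug effect. The documents do not support that. The only effect scale visible for a responder endpoint is the odds ratio stated for the 50% responder (Protocol 7.3.2, SAP 10.3). On that scale, equal random gaps shrink the effect. If placebo has more gaps, the risk difference shrinks too. This objection stands, and the point is limited accordingly.

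Second, the rule applies unless otherwise stated, and the sections where an exception would appear are redacted or largely not shown. This stands as a condition: if those sections contain an exception, the point falls away.

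Third, the size is mostly assumed. The documents give neither a completion rate nor a post-baseline mean, and varying the SD moves the full-reporting rate more than the illustrated bias does. One-day recall limits gaps, and 14 of 28 days for everyone is an extreme bound. All of this stands, but none of it changes the direction of the bias in the rate.

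Fourth, a 20-of-28 rule is not a full cure. It leaves up to 24 of 84 days unreported: if everyone were at 20 days, the model still gives 7/67 = 10.4%. It also counts participants with diary gaps as non-responders. This stands, and it is why the rule is proposed only as a check beside the prorated result.

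**Conclusion.** Under the visible rule, incomplete diaries can only bias the 100% responder rate upward. That follows from the arithmetic of proration and needs no model. The illustrated rise from 7.7% to 10.0% at 21 of 28 days rests on the assumed means, a borrowed SD and random gaps; it would be larger if diaries are skipped more often on migraine days. The direction of the effect on the treatment comparison depends on the scale and on which arm misses more days.

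A reader might also infer that 14 zero days could count as 12 migraine-free weeks, because the efficacy population needs only one evaluable 4-week period (Protocol 7.1), and SAP 10.2.3 carries a discontinued participant's observed mean over the three months. SAP 10.2.3 says this about the ANCOVA. Whether the 100% endpoint uses the same derivation is not visible, so this cannot be claimed.

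The consequence is modest. The endpoint is outside the listed primary and six secondary endpoints, and no stated power figure is affected. This is a cheap improvement, not a flaw in the main analysis.

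**What to change.** First check the redacted derivation sections for an exception. If there is none, keep the prorated result for the 100% endpoint and report beside it:

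1. an analysis that multiply imputes unreported days by arm (for example from a beta-binomial fit) and requires zero migraine days over all 84 days;
2. a simple check that counts as responders only participants with no reported migraine day and at least 20 of 28 days reported in each of the three windows, which is the plan's own baseline standard.

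Report diary completion by arm, so that readers can judge how much the gaps matter. Leave the mean-count, 50% and 75% analyses unchanged.

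The cost is a short SAP addition and a little programming. The migraine-free rate will be somewhat lower in the added analyses, and in the completeness check some truly migraine-free participants with diary gaps will count as non-responders.
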